4. AKI
5. AKI requiring dialysis
6. Vascular access site complications including pseudoaneurysm, AV fistula, retroperitoneal bleed

CABG:

1. Return to operating room for bleeding
2. Prolonged intubation
3. Mediastinitis
4. Atrial fibrillation
5. AKI requiring dialysis

In addition the incidence of finding significant LM stenosis ($\geq 50\%$) on cardiac catheterization will be monitored and reported to the DSMB.

2. Events occurring in the time period between consent and randomization

In general, eligibility for randomization will not be known at the time of enrollment but will need to be confirmed after performing additional screening procedures (e.g. pregnancy test). As a result, several days may elapse before the participant is randomized. Frequency of clinical events (e.g. death, MI) occurring during this time period, prior to randomization, will be monitored and reported to the DSMB.

3. Events that are trial endpoints

Selected trial endpoints (e.g. all-cause mortality) will be monitored at regular intervals during the course of the trial for the purpose of protecting participants' safety. Event rates in each treatment group will be confidentially reviewed by the DSMB. These analyses will inform the DSMB's recommendation to stop or continue the study or modify the protocol (see [section 11.2.6](#)).

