Participants with advanced CKD are at increased risk for complications of the assigned invasive procedure, specifically contrast-induced acute kidney injury (AKI),^{15,16} dialysis, major bleeding and short-term risk of death. However, there is controversy in the medical literature regarding the incidence (<1% to >30%), effective treatment (saline hydration, N-acetyl cysteine, or sodium bicarbonate) and prognosis of contrast induced AKI (<0.5% to >5% requiring dialysis).¹⁷⁻²⁰ In addition although contrast induced AKI have been associated with increase in short-term mortality residual confounding in these studies makes interpretation difficult. Moreover it is unknown if these short-term increased risks are offset by long-term benefits. Limited observational study in the CKD cohort suggests a survival benefit of revascularization when compared with medical therapy alone long-term,²¹⁻²⁴ despite increase in short-term risks. However, the medical therapy in these trials was not optimized, drug eluting stents were rarely used and there is undoubtedly inherent selection and ascertainment bias with observational studies. The above has resulted in **substantial clinical equipoise in the management of these patients with the rates of revascularization of only around 10-45%.**^{21,23,25} The results of ISCHEMIA-CKD will have profound implications for guidelines, health policy, and clinical practice.

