1. LVEF <35%
2. History of unprotected left main stenosis \geq 50% on prior coronary computed tomography angiography (CCTA) or prior cardiac catheterization (if available)
3. Finding of "no obstructive CAD" (<50% stenosis in all major epicardial vessels) on prior CCTA or prior catheterization, performed within 12 months
4. Coronary anatomy unsuitable for either PCI or CABG
5. Unacceptable level of angina despite maximal medical therapy
6. Very dissatisfied with medical management of angina
7. History of noncompliance with medical therapy
8. Acute coronary syndrome within the previous 2 months
9. PCI within the previous 12 months
10. Stroke within the previous 6 months or spontaneous intracranial hemorrhage at any time

11. History of ventricular tachycardia requiring therapy for termination, or symptomatic sustained ventricular tachycardia not due to a transient reversible cause
12. NYHA class III-IV heart failure at entry or hospitalization for exacerbation of chronic heart failure within the previous 6 months
13. Non-ischemic dilated or hypertrophic cardiomyopathy
14. Severe valvular disease or valvular disease likely to require surgery or percutaneous valve replacement during the trial
15. Allergy to radiographic contrast that cannot be adequately pre-medicated, or any prior anaphylaxis to radiographic contrast
16. Planned major surgery necessitating interruption of dual antiplatelet therapy (note that patients may be eligible after planned surgery)
17. Life expectancy less than the duration of the trial due to non-cardiovascular comorbidity
18. Pregnancy (known to be pregnant; to be confirmed pre- randomization, if applicable)
19. Patient who, in the judgment of the patient's physician, is likely to have significant unprotected left main stenosis
20. Enrolled in a competing trial that involves a non-approved cardiac drug or device
21. Inability to comply with the protocol
22. Exceeds the weight or size limit for cardiac catheterization at the site
23. Canadian Cardiovascular Society Class III angina of recent onset, or angina of any class with a rapidly progressive or accelerating pattern
24. Canadian Cardiovascular Society Class IV angina, including unprovoked rest angina
25. High risk of bleeding which would contraindicate the use of dual antiplatelet therapy
26. Cardiac transplant recipient

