13.2 Risks and Benefits

All procedures and tests performed in this study are commonly performed in clinical practice and have well defined safety profiles. Furthermore, all procedures performed in this study, are commonly performed for the patient population enrolled in the study, i.e., those with advanced CKD, SIHD and at least moderate ischemia. The risk of cath and revascularization will be minimized by the selection of experienced operators who meet study certification criteria. These risks are justified by the potential benefit (long-term reduction in events resulting from revascularization, as discussed in the background section).

Risks:

Cath/PCI/CABG Risks: Each of these procedures is performed in clinical practice for patients who meet eligibility criteria for the CKD trial. The major risks of these procedures include death, myocardial infarction and stroke. Other risks of catheterization and PCI include severe contrast reaction such as anaphylaxis, emergency CABG, bleeding, need for blood transfusion, contrast-induced AKI, AKI requiring dialysis and vascular access site complications including pseudoaneurysm, AV fistula, retroperitoneal bleed or infection. Other risks of CABG include return to operating room for bleeding, need for blood transfusion, infection, prolonged intubation, mediastinitis, AKI, AKI requiring dialysis and atrial fibrillation. Risks of these procedures vary in likelihood based on the patient's risk profile and are generally higher in the CKD cohort than in participants without CKD.

Risk Lowering Measures:

The risk of cath and revascularization will be minimized by the selection of experienced operators who meet study certification criteria. Strategies to minimize the volume of contrast used and reduce the risk of contrast-induced AKI are outlined in the MOO. These risks are

justified by the potential benefit (long-term reduction in events resulting from revascularization, as discussed in the background section). Study procedures are designed to manage and minimize risks through careful selection of the patients who participate in the trial. Participants will be monitored closely through the trial at many time points to check on their health. In addition, an independent DSMB will monitor safety of the participants throughout the study (see [section 13.1](#))

Benefits:

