13.3 Safety Monitoring Objectives and Rationale

The main safety objectives in ISCHEMIA-CKD are to characterize the risk profiles of the two randomized management strategies and to monitor for unanticipated risks to study participants. All medications and procedures to be used/performed in this study are commonly used/performed for clinical indications as part of standard of care and have well-defined safety profiles. Because no investigational device, drug, diagnostic test or therapeutic intervention is being tested in this comparative effectiveness trial, reporting is primarily governed by the Common Rule (45 CFR Part 46, Subpart A), as well as ICH Guidelines, IRBs and local regulations.

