13.5 Events to be Monitored

Safety monitoring in ISCHEMIA-CKD will be concerned with estimating event rates for the following types of clinical events:

1. Complications of cardiovascular tests (e.g. cardiac catheterization) and therapeutic procedures (e.g. PCI, CABG)
2. Events occurring in the time period between consenting to participate in the trial and being randomized.
3. Study endpoints.

1. Complications of cardiovascular tests and therapeutic procedures

All drugs, diagnostic tests and therapeutic procedures to be used in this trial have been extensively evaluated previously, have established safety profiles with known risks and benefits and are routinely used in clinical practice. Events listed below occurring within 72 hours of the procedure will be considered as a complication of the procedure. Some safety events related to specific tests and procedures captured within EDC, in addition to death and MI, include:

Cardiac catheterization and PCI:

1. Severe contrast reaction such as anaphylaxis
2. Periprocedural stroke
3. Emergency CABG

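### Major bleeding is named as a specific risk of the invasive procedure, but section 13.5 lists it only as two kinds of procedural event and no comparison by randomized arm is planned

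*Combined protocol and SAP*

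**What the plan says.** Protocol section 2 (Background and Rationale) lists the complications for which participants with advanced CKD are at increased risk from the invasive procedure. After contrast-induced acute kidney injury (AKI) it gives "dialysis, major bleeding and short-term risk of death". It adds that nobody knows whether these short-term risks are offset by long-term benefit.

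Section 13.2 (Risks and Benefits) includes "emergency CABG, bleeding, need for blood transfusion, contrast-induced AKI, AKI requiring dialysis and vascular access site complications" among the risks of catheterization and PCI. Bleeding and transfusion thus stand there separately from access-site problems. Its CABG list includes reoperation for bleeding and, again, transfusion.

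Section 13.3 states as a main safety objective to "characterize the risk profiles of the two randomized management strategies".

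Section 13.5 (Events to be Monitored) gives the attribution rule: "Events listed below occurring within 72 hours of the procedure will be considered as a complication of the procedure". The list opens with "Some safety events related to specific tests and procedures captured within EDC, in addition to death and MI, include". Under catheterization and PCI the only item that covers bleeding is "Vascular access site complications including pseudoaneurysm, AV fistula, retroperitoneal bleed"; under CABG it is reoperation for bleeding. Review of rates by treatment group is stated there only for trial endpoints.

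Bleeding is not among the secondary endpoints (sections 3 and 11.2.2), the adjudicated events (section 10) or the outcomes on which interim comparisons by strategy focus (section 11.2.6). Section 13.4 adds no study-specific reporting beyond the EDC data.

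**The concern.** The protocol's case for the trial is a trade-off: short-term procedural harm against possible long-term gain. Bleeding is one of the harms it puts on that scale. The others in the same sentence of section 2 (AKI, dialysis, death) each reappear by name in section 13.5. Major bleeding does not.

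A list of complications after procedures, even a complete one, cannot give the difference between strategies. Its denominator is people who had a procedure, a group defined after randomization and made up differently in the two arms. The contrast that section 13.3 asks for needs all randomized participants, counted from randomization, in the arm to which they were assigned.

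Followed as written, the plan could deliver a randomized estimate for death or MI with no matching estimate for a harm that the protocol itself names. Readers weighing the two strategies would have to piece bleeding together from procedural complications and uncategorized admissions.

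**Working it through.** **Step 1. Follow bleeding through the documents.**

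| Place | What is said about bleeding |
|---|---|
| Section 2 | Major bleeding is a specific risk of the invasive procedure |
| Section 13.2, cath/PCI | Bleeding; transfusion; access-site complications |
| Section 13.2, CABG | Reoperation for bleeding; transfusion |
| Section 13.5, cath/PCI | Access-site complications only (retroperitoneal bleed given as an example) |
| Section 13.5, CABG | Reoperation for bleeding only |
| Sections 3, 10, 11.2.2, 11.2.6 | No bleeding endpoint, adjudicated bleeding event or interim bleeding comparison |

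General bleeding (cath/PCI) and transfusion (both lists) drop out between 13.2 and 13.5.

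**Step 2. Ask where a bleed outside the 72-hour window would go.** Section 9 collects a hospitalization assessment on all randomized participants at each follow-up, as a measure of resource use. A hospitalized bleed enters the database there, as an admission. A fatal bleed enters all-cause death, with cause adjudicated (section 10). A transfused bleed without admission has no stated place. None of these routes is an analysis of bleeding by arm.

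**Step 3. Check the sample size used for scale.** The documents give no bleeding figure to reproduce. The power table in section 11.1.1 assumes 500 per group, 3.7 years of average follow-up and 1% loss per year. Its headline row does reproduce. With exponential hazards, a 60% rate in CON and a 15% relative reduction (51% in INV), HR = ln(0.49)/ln(0.40) = 0.779 and about 519 events are expected. Then z = (√519/2) × |ln 0.779| − 1.96 ≈ 0.89, which is power of 81.4% against the stated 81%. For reductions of 17% and 19% the results are 89.7% and 95.0%, against 90% and 95%. So 500 per arm is a sound base.

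**Step 4. Precision of a by-arm bleeding estimate.** The proportion p with a qualifying bleed is an assumption, taken equal in both arms. Half-width of the 95% interval for the difference = 1.96 × √(2p(1−p)/500).

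- p = 5%: 1.96 × √0.00019 = 2.7 points
- p = 10%: 1.96 × √0.00036 = 3.7 points
- p = 15%: 1.96 × √0.00051 = 4.4 points

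**Step 5. What it could detect.** For a two-proportion comparison with 500 per arm and two-sided 0.05:

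| Assumed CON rate | INV rate detectable with 80% power | Risk ratio | Power for a risk ratio of 1.5 |
|---|---|---|---|
| 5% | about 9.7% | 1.93 | 37% |
| 10% | about 16.0% | 1.60 | 67% |
| 15% | about 21.9% | 1.46 | 86% |

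The trial would estimate a bleeding difference usefully, but would reliably detect a moderate one only if bleeding is common. These binomial figures ignore competing mortality. Section 2 projects 4-year mortality above 50%, so the analysis itself must allow for it.

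**The case against.** The strongest reply is that the gap is narrower than it looks, and much of that stands.

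- *The list is open.* Section 13.5 introduces its items as examples, and the access-site line is itself wider than retroperitoneal bleeding. One can say only that these are the bleeding events named, not that no others would be recorded.
- *CON participants can contribute.* A reader might infer that bleeds are counted only in INV. That is wrong: section 13.5 is organized by procedure, and sections 6.1 and 6.6 foresee catheterization and revascularization in CON.
- *The DSMB is not blind to it.* Section 13.1 lets its reports carry additional safety events and anything else it requests, and admissions are recorded in both arms. A reader might infer that an excess could not be seen; the documents do not support that. What is missing is a defined event and a planned table.
- *The 72 hours is an attribution window.* It restarts with each procedure, so setting three days against the whole of follow-up would misstate coverage.
- *Later bleeding on antiplatelet drugs is an inference.* Section 2 speaks of the procedure and of short-term risk. Dual antiplatelet therapy appears only in the exclusion criteria, for example "High risk of bleeding which would contraindicate the use of dual antiplatelet therapy", with no duration or use by arm, and section 6.3 applies medical therapy equally to both groups. A lasting difference in exposure between arms is not stated.
- *Other documents may cover it.* The Manual of Operations, DSMB analysis plan, DSMB and event-committee charters and final SAP are not available here.
- *Light safety collection is deliberate.* Section 13.3 points out that no investigational product is tested.

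These points limit the claim but do not remove it. Open wording is not a pre-specified analysis, and the objective in 13.3 concerns the strategies as randomized.

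**Conclusion.** The concern holds in a limited form. Sections 2 and 13.2 name bleeding as a risk, section 13.5 names only access-site complications and reoperation for bleeding within 72 hours of a procedure in either arm, and no comparison by randomized arm is planned in these documents. That falls short of the safety objective in section 13.3. It does not affect the primary analysis or its power.

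The size of any bleeding difference cannot be stated, because the documents give no rate. What can be stated is the precision on offer: about ±2.7 to ±4.4 percentage points for assumed rates of 5% to 15%, with 500 per arm and competing death ignored. A reader might take this to mean that the trial can settle the bleeding question at its present size. It cannot promise that: at an assumed 5%, power for a risk ratio of 1.5 is only 37%. The gain is an unconfounded estimate with an interval, where none is now planned. This is a cheap and worthwhile improvement, not a flaw that undermines the trial.

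**What to change.** 1. Add bleeding and transfusion to the procedural lists in section 13.5 so that they match section 13.2.
2. Add one pre-specified safety event to section 13.5: bleeding leading to hospitalization, transfusion or death, in all randomized participants from randomization to closeout. Use the existing hospitalization assessment and the adjudicated cause of death, plus one form item on transfusion given for a bleed.
3. Report it by randomized arm in DSMB reports and in the final safety analysis, as cumulative incidence with a 95% confidence interval for the difference, treating death without a qualifying bleed as a competing event. Label it as estimation, with no significance claim.
4. If the Manual of Operations, DSMB plan or final SAP already does this, a cross-reference in section 13.5 is enough.

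The cost is a protocol line, one item at existing visits and one table; no extra visit, test, participant or change to treatment is needed. Section 11.2 says that the SAP is still to be finalized, so there is room for the analysis. The downside is a little more data entry, and investigator-reported, unadjudicated bleeding in an open-label trial carries some reporting bias. The hospitalization or transfusion threshold limits that bias but does not remove it, and the report should say so.

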14. ETHICAL CONSIDERATIONS

14.1 Regulatory and Ethical Compliance

This clinical study was designed and shall be implemented and reported in accordance with the international conference on harmonization (ICH) Harmonized Tripartite Guidelines for Good Clinical Practice, with applicable local regulations (including European Directive 2001/20/EC, US Code of Federal Regulations Title 45 and Japanese Ministry of Health, Labor, and Welfare), and with the ethical principles laid down in the Declaration of Helsinki.

14.2 Informed Consent Process

Investigators must ensure that participants are clearly and fully informed about the purpose, potential risks, and other critical issues regarding clinical studies in which they volunteer to participate. Freely given written informed consent must be obtained from every participant or, in those situations where consent cannot be given by participants, their legally acceptable representative, prior to clinical study participation. The rights, safety, and well-being of the study participants are the most important considerations and should prevail over interests of science and society. Women of child bearing potential will be informed that there may be unknown risks to the fetus if pregnancy were to occur during the study and they were exposed to radiation (e.g. cardiac catheterization and revascularization if randomized to the INV strategy group) and agree that in order to participate in the study they must adhere to the contraception requirement during this period of the study. If there is any question that the prospective participant will not reliably comply with study procedures and/or follow-up, they should not be entered in the study.

14.3 Responsibilities of the Investigator and IRB/IEC/REB

The protocol and the proposed informed consent forms (main consent form and genetics testing consent form) will be reviewed and approved by a properly constituted Institutional Review Board/Independent Ethics Committee/Research Ethics Board (IRB/IEC/REB) at each site. A signed and dated statement that the protocol and informed consent have been approved by the IRB/IEC/REB is required before site initiation. Prior to study start, the site principal investigator is required to sign a protocol signature page confirming his/her agreement to conduct the study in accordance with these documents and all of the instructions and procedures found in this protocol and to give access to all relevant data and records to monitors, auditors, Clinical Quality Assurance representatives, designated agents of CCC, IRBs/IECs/REBs, and regulatory authorities as required. Investigators must agree to apply due diligence to avoid protocol deviations.

14.4 Protocol Amendments

Any change or addition to the protocol can only be made in a written protocol amendment that must be approved by CCC, Health Authorities where required, and the IRB/IEC/REB. Only amendments that are required for participant safety may be implemented prior to IRB/IEC/REB approval. As soon as possible, the implemented deviation or change, the reasons for it and, if appropriate, the proposed protocol amendment(s) will be submitted: (a) to the IRB/IEC/REB for

review and approval/favorable opinion; (b) to the sponsor, NIH/NHLBI for agreement; and, if required, (c) to the regulatory authority(ies). Notwithstanding the need for approval of formal protocol amendments, the investigator is expected to take any immediate action required for the safety of any participant included in this study, even if this action represents a deviation from the protocol. In such cases, CCC should be notified of this action and the IRB/IEC/REB at the study site should be informed.

14.5 Early Termination of the Study

The CCC and NHLBI retain the right to terminate the study, a study site or an investigator at any time. The CCC will monitor the progress of the study. If warranted, the study may be suspended or discontinued early if there is an observation of safety concerns posing an unreasonable risk to the study population. If the study is terminated early, the CCC will provide a written statement to the site Principal Investigators to enable notification to site IRBs/IECs/REBs and study participants. The CCC will also inform the appropriate Competent Authorities. The CCC may terminate enrollment activity at a site, or participation in the study by the investigator and site if there is evidence of an investigator's failure to maintain adequate clinical standards or failure to comply with the protocol. Notification of enrollment suspension or termination of the study or study site/investigator will be sent to the investigator and the IRBs/IECs/REBs.

